11.4.1.2. Serious Adverse Events

A serious adverse event (SAE) is defined as an adverse event that meets any of the following criteria:

1. Results in death.
2. Is life threatening: that is, poses an immediate risk of death as the event occurred.
 - a. This serious criterion applies if the study subject, in the view of the Site Investigator or Sponsor, is at immediate risk of death from the AE as it occurs. It does not apply if an AE hypothetically might have caused death if it were more severe.
3. Requires inpatient hospitalization or prolongation of existing hospitalization.
 - a. Hospitalization for an elective procedure (including elective PEG tube/g-tube/feeding tube placement) or a routinely scheduled treatment is not an SAE by this criterion because an elective or scheduled “procedure” or a “treatment” is not an untoward medical occurrence.
4. Results in persistent or significant disability or incapacity.
 - a. This serious criterion applies if the “disability” caused by the reported AE results in a substantial disruption of the subject’s ability to carry out normal life functions.
5. Results in congenital anomaly or birth defect in the offspring of the subject (whether the subject is male or female).

6. Necessitates medical or surgical intervention to preclude permanent impairment of a body function or permanent damage to a body structure.
7. Important medical events that may not result in death, are not life-threatening, or do not require hospitalization may also be considered SAEs when, based upon appropriate medical judgment, may jeopardize the subject and may require medical or surgical intervention to prevent one of the outcomes listed in this definition. Examples of such medical events include blood dyscrasias or convulsions that do not result in inpatient hospitalization, or the development of drug dependency or drug abuse.

An inpatient hospital admission in the absence of a precipitating, treatment-emergent, clinical adverse event may meet criteria for "seriousness" but is not an *adverse* experience, and will therefore, not be considered an SAE. An example of this would include a social admission (subject admitted for other reasons than medical, e.g., lives far from the hospital, has no place to sleep).

A serious, suspected adverse drug reaction is an SAE that, in the opinion of the Site Investigator or Sponsor, suggests a reasonable possibility that the investigational product caused the event.

The Site Investigator is responsible for classifying adverse events as serious or non-serious.

11.4.2. Assessment and Recording of Adverse Events

This study will utilize the CTCAE version 4.0 coding system for adverse event recording. Adverse events reported using CTCAE will be recoded into MedDRA terms by the DCC.

Assessment of Adverse Events

At each visit (including telephone interviews), the subject will be asked "Have you had any problems or symptoms since your last visit?" in order to determine the occurrence of adverse events. If the subject reports an adverse event, the Investigator will determine:

1. Type of event
2. Date of onset and resolution (duration)
3. Severity (mild, moderate, severe)
4. Seriousness (does the event meet the above definition for an SAE)
5. Causality, relation to investigational product and disease
6. Action taken regarding investigational product
7. Outcome

Relatedness of Adverse Event to Investigational Product

The relationship of the AE to the investigational product should be specified by the Site Investigator, using the following definitions:

1. Not Related: Concomitant illness, accident or event with no reasonable association with treatment.
2. Unlikely: The reaction has little or no temporal sequence from administration of the investigational product, and/or a more likely alternative etiology exists.
3. Possibly Related: The reaction follows a reasonably temporal sequence from administration of the investigational product and follows a known response pattern to the suspected investigational product; the reaction could have been produced by the investigational product or could have been produced by the subject's clinical state or by other modes of therapy administered to the subject. (suspected ADR)
4. Probably Related: The reaction follows a reasonably temporal sequence from administration of investigational product; is confirmed by discontinuation of the investigational product or by re-challenge; and cannot be reasonably explained by the known characteristics of the subject's clinical state. (suspected ADR)
5. Definitely Related: The reaction follows a reasonable temporal sequence from administration of investigational product; that follows a known or expected response pattern to the investigational product; and that is confirmed by improvement on stopping or reducing the dosage of the investigational product, and reappearance of the reaction on repeated exposure. (suspected ADR)

Recording of Adverse Events

All clinical adverse events are recorded in the Adverse Event (AE) Log in the subject's study binder. The site should fill out the AE Log and enter the AE information into the online Adverse Event Reporting System within 5 working days of the site learning of a new AE or receiving an update on an existing AE.

Please Note: Serious Adverse Events (SAEs) must be reported to the NeuroNEXT Data Coordinating Center within 24 hours of the site learning of the SAE.

Entries on the AE Log (and into the online Adverse Event Reporting System) will include the following: name and severity of the event, the date of onset, the date of resolution, relationship to investigational product, action taken, and primary outcome of event.

Adverse Events and Serious Adverse Events - Reportable Events

The following are considered reportable events and must be reported to the NeuroNEXT Data Coordinating Center within 24 hours of the site being notified of the event.

- All events that meet the above criteria for Serious Adverse Events (SAEs)

All occurrences of Serious Adverse Events (SAEs) must be reported within 24 hours of discovery of the event. All other Adverse Events (AEs) must be reported within *5 business days/7 calendar days* (of discovery of the event).

Adverse Event Data Management System (AEDAMS)

Upon entry of a serious adverse event by a clinical site, the DCC Online Adverse Event Reporting System will immediately notify the IMM. If warranted, the IMM will notify the DSMB chair.

Serious adverse events: The site investigator determines causality (definitely not related, probably not related, possibly related, probably related, definitely related) of the adverse event. The IMM will review the SAE report. The IMM may request further information if necessary. The DSMB may suggest changes to the protocol or consent form to the Project PI as a consequence of adverse events. The Online Adverse Event Reporting System maintains audit trails and stores data (and data updated) and communication related to any adverse event in the study.

Non-serious adverse events: Non-serious adverse events that are reported to or observed by the investigator or a member of his research team will be submitted to the DCC within 5 working days. The events will be presented in tabular form and given to the IMM on a quarterly basis or as requested. Local site investigators are also required to fulfill all reporting requirements of their local institutions.

The DCC will prepare aggregate reports of all adverse events (serious/not serious and expected, unexpected) for the DSMB.

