Serious adverse events: The site investigator determines causality (definitely not related, probably not related, possibly related, probably related, definitely related) of the adverse event. The IMM will review the SAE report. The IMM may request further information if necessary. The Online Adverse Event Reporting System maintains audit trails and stores data (and data updated) and communication related to any adverse event in the study. The IMM may determine that the Serious Adverse Event requires expedited reporting to the FDA. The DCC will prepare a Medwatch safety report for submission to the FDA. If warranted, the IMM will notify the DSMB chair. The DSMB may suggest changes to the protocol or consent form to the Study Chair as a consequence of adverse events.

Non-serious adverse events: Non-serious adverse events that are reported to or observed by the investigator or a member of his research team will be submitted to the DCC in a timely fashion (within 5 working days). The events will be presented in tabular form and given to the IMM on a quarterly basis or as requested. Local site investigators are also required to fulfill all reporting requirements of their local institutions.

The DCC will prepare aggregate reports of all adverse events (serious/not serious, expected/unexpected and relationship to study drug) for the IMM and the DSMB on a quarterly basis or as requested. In addition, all adverse events will be coded using the MedDRA system. A separate report detailing protocol compliance will also be available from the DCC for DSMB and/or site review monthly or as requested. The research team will then evaluate whether the protocol or informed consent document requires revision based on the reports.

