11.4.1. Definitions of Adverse Events, Suspected Adverse Drug Reactions & Serious Adverse Events

11.4.1.1. Adverse Event Collection and Reporting

Subjects will be monitored for AEs from the time they sign consent until 30 days following permanent discontinuation of study drug. Adverse events during the screening phase (from the time the subject signs consent until they are randomized) shall only include events related to study procedures, i.e. infection of skin biopsy site. If not related to study procedures, any new or worsened medical conditions reported during the screening process will be recorded in medical history.

An adverse event (AE) is any unfavorable and unintended sign (including a clinically significant abnormal laboratory finding, for example), symptom, or disease temporally associated with a study, use of a drug product or device whether or not considered related to the drug product or device.

Adverse drug reactions (ADR) are all noxious and unintended responses to a medicinal product related to any dose. The phrase “responses to a medicinal product” means that a causal relationship between a medicinal product and an adverse event is at least a reasonable possibility, i.e., the relationship cannot be ruled out. Therefore, a subset of AEs can be classified as suspected ADRs, if there is a causal relationship to the medicinal product.

Examples of adverse events include: new conditions, worsening of pre-existing conditions, clinically significant abnormal physical examination signs (i.e. skin rash, peripheral edema, etc), or clinically significant abnormal test results (i.e. lab values or vital signs), with the exception of outcome measure results, which are not being recorded as adverse events in this trial (they are being collected, but analyzed separately).

Stable chronic conditions (i.e., diabetes, arthritis) that are present prior to the start of the study and do not worsen during the trial are NOT considered adverse events. Chronic conditions that

occur more frequently (for intermittent conditions) or with greater severity, would be considered as worsened and therefore would be recorded as adverse events.

Adverse events are generally detected in two ways:

Clinical → symptoms reported by the subject or signs detected on examination.

Ancillary Tests → abnormalities of vital signs, laboratory tests, and other diagnostic procedures (other than the outcome measures: the results of which are not being captured as AEs).

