If discernible at the time of completing the AE log, a specific disease or syndrome rather than individual associated signs and symptoms should be identified by the Site Investigator and recorded on the AE log. However, if an observed or reported sign, symptom, or clinically significant laboratory anomaly is not considered by the Site Investigator to be a component of a specific disease or syndrome, then it should be recorded as a separate AE on the AE log. Clinically significant laboratory abnormalities, such as those that require intervention, are those that are identified as such by the Site Investigator.

An unexpected adverse event is any adverse event, the specificity or severity of which is not consistent with the current Investigators Brochure or package insert or described in the protocol. An unexpected, suspected adverse drug reaction is any unexpected adverse event that, in the opinion of the Site Investigator or Sponsor, there is a reasonable possibility that the investigational product caused the event.

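### The causality definitions leave no suspected-reaction grade for an event new in kind that has no dechallenge or rechallenge evidence, contrary to the protocol's own definition of an adverse drug reaction.

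*Combined protocol and SAP*

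**What the plan says.** Section 11.4.2 says that the relationship of an event to the study drug "should be specified by the Site Investigator, using the following definitions". Five grades follow: Not Related, Unlikely, Possibly Related, Probably Related and Definitely Related. Only the last three carry the label of suspected adverse drug reaction (ADR).

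Possibly Related combines plausible timing with a second condition, that the event "follows a known response pattern to the suspected investigational product".

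Section 11.4.1.1 defines ADRs more broadly. A causal link need only be "at least a reasonable possibility, i.e., the relationship cannot be ruled out". The same section foresees reactions not yet described: "An unexpected, suspected adverse drug reaction is any unexpected adverse event" for which the site investigator or the sponsor sees a reasonable possibility of causation. Section 11.4.1.2 applies the same reasonable-possibility test to serious suspected reactions.

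Section 11.4 gives a differently labelled scale: "The site investigator determines causality (definitely not related, probably not related, possibly related, probably related, definitely related) of the adverse event". That sentence recurs later in 11.4.2, under the adverse event data management system. Neither place defines those labels.

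**The concern.** Causality asks whether the drug may have caused the event. Expectedness asks whether such an event is already known for the drug. Section 11.4.1.1 keeps the two questions apart, but Possibly Related in 11.4.2 makes a known pattern part of the causality answer. The lowest suspected-ADR grade is where a site would naturally place a new kind of reaction with little supporting evidence, and its wording excludes that reaction.

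The grade is used downstream. Relationship to study drug is a required entry in the adverse event log and the online system (11.4.2). It is a breakdown variable in the aggregate reports for the IMM (10.2) and for the IMM and DSMB (11.4). If sites improvise when no definition fits, the same event may be graded differently at different sites, and suspected reactions may be undercounted.

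**Working it through.** No arithmetic applies. The check is to take one defined event and test it against each grade in 11.4.2.

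**Test event:** plausible timing after dosing; no more likely alternative cause; not a recognised topiramate reaction; no dechallenge or rechallenge evidence, for example because it was fatal, irreversible or resolved while the drug continued.

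| Grade (11.4.2) | Suspected ADR? | What the grade requires | Test event |
|---|---|---|---|
| Not Related | No | No reasonable link to treatment | Does not fit: the timing gives a reasonable link |
| Unlikely | No | "The reaction has little or no temporal sequence from administration of the investigational product, and/or a more likely alternative etiology exists" | Does not fit: the timing is plausible and nothing else is likelier |
| Possibly Related | Yes | Plausible timing, and "follows a known response pattern to the suspected investigational product"; the drug, the clinical state or another therapy could each be the cause | Fails on pattern |
| Probably Related | Yes | Plausible timing; "is confirmed by discontinuation of the investigational product or by re-challenge"; not reasonably explained by the clinical state | Fails on confirmation |
| Definitely Related | Yes | Plausible timing; "that follows a known or expected response pattern to the investigational product"; improvement on stopping or reducing the drug; return on re-exposure | Fails on pattern, dechallenge and rechallenge |

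Result: 0 of the 3 suspected-ADR grades and, read literally, 0 of all 5.

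**Same event under 11.4.1.1.** The timing is plausible and no other cause is more likely, so a causal link cannot be excluded. The event is a suspected ADR under that definition. The two sections therefore give different answers for the same event.

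**Limits of the gap.**
- A novel event with positive dechallenge that the clinical state does not reasonably explain meets Probably Related, which has no pattern condition.
- If such an event also has a reasonable, though not likelier, explanation in the clinical state, it fails Probably Related and again has no grade.
- Section 11.4.1.1 counts an event as unexpected by its specificity or by its severity. An unusually severe form of a known reaction can still follow a known pattern and be Possibly Related.

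The gap is thus confined essentially to events new in kind that lack confirming dechallenge or rechallenge evidence.

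**Labels.** There are two scales. The top three labels agree. The bottom two differ: Not Related and Unlikely in the defined list, against definitely not related and probably not related in 11.4 and the later part of 11.4.2. This mismatch does not move the suspected-ADR cut-off, but it leaves two labels undefined.

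**The case against.** The strongest reply is that the safety system does not rest on this grade, and most of that reply stands.

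- **Expedited reporting.** A reader might infer that a novel serious reaction could be lost from expedited reporting under the stated rules. The documents do not support that. Every serious adverse event is due within 24 hours whatever its grade (11.4, 11.4.2). The IMM is notified at once, reviews the report and may decide that it needs expedited submission to the FDA (11.4). The sponsor's opinion also counts (11.4.1.1, 11.4.1.2). What remains is a risk if the IMM or sponsor relies on the site's grade, since no text says how that grade enters the decision.
- **Forced downgrading.** A reader might infer that sites must grade such an event below Possibly Related. Nothing compels this, because the event does not fit Unlikely either. A site could resolve the gap upward by relying on 11.4.1.1.
- **Non-serious events.** A reader might infer that these escape the IMM. Section 10.2 has the IMM review all adverse events periodically, and 11.4 sends tables of non-serious events quarterly or on request. The expedited route in 11.4 concerns serious events only.
- **DSMB.** Section 10.2 gives the DSMB partially unblinded data and has it monitor adverse event rates. Overall event rates do not depend on site attribution.

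None of this removes the contradiction between the grading definitions and the ADR definition, or its effect on the relatedness breakdown.

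**Conclusion.** The point holds as a defect in the definitions, of minor severity. Section 11.4.2 gives no suspected-ADR grade to a class of events that 11.4.1.1 and 11.4.1.2 treat as suspected reactions. The consequence is inconsistent or understated relatedness grading in the adverse event log and in the aggregate reports by relationship to drug.

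The number of events cannot be predicted from the documents. It would be too strong to say that unexpected suspected reactions as a class are defined away: unexpectedly severe forms of known reactions, and novel events with positive dechallenge not explained by the clinical state, still have a grade.

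The conclusion assumes that sites apply the five definitions as written. Sites that already grade by the broader standard in 11.4.1.1 will show less of the problem, at the price of departing from 11.4.2. Efficacy analysis, sample size and trial design are unaffected.

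**What to change.** 1. In 11.4.2, delete the known-pattern condition from Possibly Related. Define the grade by plausible timing together with a causal link that cannot be excluded, to match 11.4.1.1.
2. Judge expectedness as a separate item, as 11.4.1.1 already does.
3. Use one defined five-level scale in 11.4, in both parts of 11.4.2 and in the online reporting system.
4. Add a sentence on how the site's grade enters the IMM's decision on expedited reporting.

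The cost is protocol wording, changed pick-list labels and a memo to sites. The downside is that slightly more events will be rated possibly related.

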12. HUMAN SUBJECTS

Documented approval from the NeuroNEXT CIRB will be obtained for all participating centers prior to clinical trial start, according to ICH GCP, local laws, regulations and organization. When necessary, an extension, amendment or renewal of the CIRB approval must be obtained.

Evidence of training in responsible conduct of research shall be on file for each CSS PI and co-investigator.

12.1. Institutional Review Board (IRB) Review and Informed Consent

This protocol and the informed consent document (Appendix A) and any subsequent modifications will be reviewed and approved by the NeuroNEXT CIRB responsible for oversight of the study. A signed consent form, approved by the NeuroNEXT CIRB, will be obtained from the subject. The consent form will describe the purpose of the study, the procedures to be followed, and the risks and benefits of participation. A copy of the consent form will be given to the subject and this fact will be documented in the subject's record.

12.2. Subject Confidentiality

All laboratory specimens, evaluation forms, reports, video recordings, and other records that leave the clinical study site will be identified only by the study specific Subject Identification Number (SID) to maintain subject confidentiality. All records will be kept in a locked file cabinet. All computer entry and networking programs will be done using study specific SIDs only. Clinical

NN108 Topiramate as a Disease Modifying Therapy for CSPN

Version 8.0

Version date 8/8/2018

information will not be released without written permission of the subject, except as necessary for monitoring by CIRB, the FDA, the NINDS, the OHRP, the sponsor, or the sponsor's designee.

12.3. Study Modification/Discontinuation

The study may be modified or discontinued at any time by the CIRB, the NINDS, the sponsor, the OHRP, the FDA, or other government agencies as part of their duties to ensure that research subjects are protected.

13. PUBLICATION OF RESEARCH FINDINGS

Publication of the results of this trial will be governed by the policies of the NeuroNEXT Network and procedures developed by the NeuroNEXT Data Sharing and Publication Committee. Any presentation, abstract, or manuscript will be made available for review by the sponsor and the NINDS prior to submission.

Urine pregnancy test		X								
Functional and mobility testing (6MWT, TUG, ABC Scale)		X		X		X		X		X
Randomization		X								
Study drug dispensing		X	X	X	X	X	X			
Study drug reconciliation			X	X	X	X	X	X		X
Neuropathy symptom scales (NTSS-6, BPI-DN)		X	X	X	X	X	X	X		X
NQOL-DN	X		X	X	X	X	X	X		X
UENS	X		X	X	X	X	X	X		X
C-SSRS	X	X	X	X	X	X	X	X	X	X
RAPA		X		X		X		X		X
Concomitant medications	X	X	X	X	X	X	X	X	X	X
Adverse event review	X ⁵	X	X	X	X	X	X	X	X	X
ECG	X									
DNA sample		X								

⁵ AEs to be collected at screening **only** for events related to study procedures (e.g., skin biopsy)
